- c. Record the Date Randomized, UI number, and Condition in the 'Randomization' tab in the Summative Tracking DB
- d. Email Research Assistant once participant is randomized

Step 6: Therapist Warm Phone Call & Baseline Survey

1. If they don't pick up, leave a voicemail and send appropriate email, script below.
2. Call them back every 2 days until you reach them.

Voicemail Script:

Hi this is _____ from the Depression Treatment Study. Sorry we missed you. Thanks so much for submitting your consent form and enrolling in our study! We would love to schedule a time to tell you more about the study and the next steps of your participation. We are eager to get started and I hope to schedule a time to talk with you soon. Please give us a call back at (phone #) when you have 10-15 minutes for a quick call or let us know when a good time for us to call you back would be.

3. If they call you back
 - a. And it is a good time for you to talk: Go through the script below
 - b. And it is not a good time for you to talk: Schedule a time you can call them back.
 - i. Log call time and date in the Pilot RCT Calendar
 - c. Log the call in the cover sheet
4. If they pick up, use the script below:

Warm Call & Baseline Script:

<<customize as needed for pilot therapists>>

Hi, this is _____ and I'm calling from the Depression Treatment Study. Thank you for completing our consent form and enrolling in the the study! We would like to briefly review the study procedures and let you know what the next steps are for your participation. Is this a good time to talk?

If it is, proceed.

If not, schedule a time to call back later. [Log the call in the tracking sheet, update the date of the call in both tracking sheet and database, and enter this new date into the calendar]

We are super excited that you decided to participate in this study! As a reminder, this study will compare how clients respond to different ways of delivering treatment for depression. You have been randomly assigned to the **[Standard Care or WILLOW]** condition.

WILLOW Full RCT Therapist Protocol

<<For pilot therapists enrolling again: *You will still be assigned to [Standard Care or WILLOW] condition*>>

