We will ask that you complete three additional study assessments for each study patient you treat. These will take place at weeks 4, 8, and 12 of your patient's study treatment. We've worked to keep the study assessments as convenient as possible. Surveys at Weeks 4 and 8 will consist of a brief phone interview lasting approximately 10-15 minutes and then an online survey that may take about 15-20 minutes. You will be compensated \$50 for each week 4 and 8 survey you complete. The Week 12 assessment will consist of a phone interview that will last about 30 minutes and the online survey that will take another 30 minutes. You will be compensated \$60 for each week 12 survey you complete. During your final study assessment, you will be asked to provide information about the exact number of sessions you conducted with each of your study patients. In order to help you track these assessments, we will provide you with a session tracking sheet for your convenience.

<<for pilot therapists make sure to point out that we will not be doing amazon giftcards anymore, both for therapists and patients>>

If WILLOW Condition:

WILLOW Full RCT Therapist Protocol

<<if therapist did pilot, then they do not need to do the feature review. Skip to last paragraph>>
After our next call, we will provide you access to WILLOW and the training resources. We will also work with you to come up with a tailored training plan to meet your learning style and needs so that you can feel prepared to use WILLOW in-session. Once you have explored WILLOW and understand how to use it, we will schedule a WILLOW Feature Review with one of our study staff and ask that you demonstrate some of the WILLOW features to us. (Don't worry, you can retake the feature review up to 2 times and we will provide you with a study guide!). You'll receive \$100 for passing this review. After you complete the feature review, you will be ready for your first study patient to use WILLOW with.

Again, we will review the study procedures in depth during our next call, but do you have any questions about this right now?

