If your patient exits therapy before the 12-week study trial is over, that is okay. Neither the patient nor the therapist will be removed from the study. If this happens with any of your patients, we will still ask both you and your patient complete your post surveys and you will be paid in full upon completion of the surveys. Similarly, if any sessions are skipped or rescheduled, we will still ask you both to complete the assessments as planned.

After the week 12 survey is completed, you and your clinic will decide the next steps for the patient and if more treatment is indicated or requested, whether or not you continue with the patient outside of the study or if they will be assigned to a non-research therapist.

Do you have any questions at this point?

Describe goal of Full RCT (for both conditions):

- To give you an overview, the purpose of this full randomized controlled trial (RCT) is to test WILLOW, our computer-assisted therapy tool, and how it can be used to assist therapists to treat their patients who are experiencing depression. Additionally, we will also assess the wellbeing of both you and your patient. .

Any questions?

Describe Next Steps:

For CAU Condition Only: Skip to Step 9

<<For pilot WILLOW therapists briefly note:

- The account activation link no longer expires, but please ask your research patients to try to complete the activation as soon as possible.
- Email reminders for measures are sent the day before the due date and there is no email reminder for homework items you manually entered in WILLOW.

WILLOW Full RCT Therapist Protocol

- New feature: RCI, reliable change index, that tells you whether the change in score for a particular measure is significant.
- Your patients using WILLOW (either research patients or non-research patients) can login to WILLOW anytime to complete measures or homework, once they have activated their account, and do not need to wait for an email to prompt them.
- If they are experiencing technical difficulties, please direct them to contact our customer support ([contact]). They can also use the green Feedback & Support tab in WILLOW to contact us.

Skip to Step 9 or schedule a refresher review if needed: Now, how are you feeling about using WILLOW? Do you feel that you would need another review with me to refresh your memory?>>

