PracticeGround: Transforming Training and Delivery of Mental Health EBPs

NCT02314624 | Statistical Analysis Plan | February 8, 2020

Analysis Strategy

We conducted all analysis in IBM SPSS V19. We used the Generalized Linear Model to examine the between-condition change over time on study outcomes. The effects of primary interest were those reflecting the effects of WILLOW. For outcomes measured at baseline and follow-up points, that was the Time X Condition effects (measuring between-condition change from baseline). For outcomes measured only at follow-up points (e.g., therapeutic alliance and use of evidence-based therapy tasks), that was the Condition effects since they would represent average between-condition differences during the time patients received services. As previously mentioned, providers completed questionnaires for each study patient they treated. Hence, the provider sample size reflects the number of patients they answered about, not the number of providers. Several providers participated in the study concurrently with multiple patients. Patients were included in the analyses only if they attended five or more sessions with a participant provider.

Preliminary analyses provided important information guiding our strategy. First, we found no statistically significant differences between conditions on baseline measures. Second, we computed the design effects due to this nested design to determine the extent to which the intraclass correlation due to clustering and size of the cluster affected the analyses. Design effects ranged up to 1.8. Because all were under 2.0, we did not adjust analyses to account for clustering effects (Muthén & Satorra, 1995). For providers meeting participating in both studies, we used their Study 1 data for outcomes except for outcomes measured only in Study 2. For those outcomes, we used their Study 2 data.

References

Muthén, B.O. & Satorra, A. (1995). Complex sample data in structural equation modeling. *Sociological Methodology*, 25, 267-316. doi: 10.2307/271070

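### The SAP's rule for providers in both studies implies that Study 1 and Study 2 records are analysed together, but it names no Study term and gives no counts by study and condition

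*SAP*

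**What the plan says.** The SAP's Analysis Strategy names two effects of primary interest. For outcomes measured at baseline and follow-up it is Time X Condition. For outcomes measured only at follow-up, such as alliance, it is Condition. The SAP then refers, without definition or dates, to a Study 1 and a Study 2. For providers who were in both, it states: "we used their Study 1 data for outcomes except for outcomes measured only in Study 2". The exception follows: "For those outcomes, we used their Study 2 data". It mentions no Study factor, no stratification by study and no by-study display, and it does not set out the full model. Patients count only if they attended at least five sessions.

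The Therapist Protocol describes a full RCT that some pilot therapists re-join. In Step 6 the script tells them "You will still be assigned to" their existing condition, and staff are to "make sure to point out that we will not be doing amazon giftcards anymore, both for therapists and patients". In Step 7 the note for returning WILLOW therapists lists "New feature: RCI, reliable change index, that tells you whether the change in score for a particular measure is significant", and says that the account activation link has stopped expiring. No passage says that Study 1 is the pilot and Study 2 the full RCT, but that is the natural reading.

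**The concern.** Choosing one study's record for a provider who was in both is a de-duplication step. It is needed when the two studies' records share an analysis and serves little purpose otherwise. For outcomes common to both studies, the condition comparison therefore probably rests on a mixture of records collected under two sets of study conditions. That the sets differed in at least one respect is plain from the SAP, since some outcomes were "outcomes measured only in Study 2".

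If WILLOW records come from Study 1 more often than control records do, or less often, any difference between the studies that affects the outcome becomes part of the apparent WILLOW effect. Without the counts, a reader cannot tell whether that happened. A separate issue arises on the pilot/full-RCT reading: the software changes reach only the WILLOW arm, so the combined estimate would average over two versions of the intervention.

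Outcomes measured only in Study 2 are single-study analyses and lie outside this point.

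**Working it through.** **No stated figure to reproduce.** The documents give no sample size, no records per study, no study-by-arm counts and no effect sizes. The only numerical result in the SAP, design effects up to 1.8, concerns clustering. The numbers below are illustrations on assumed inputs.

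**Step 1: what is being biased.** Let d be the between-study difference in SD units, and pW and pC the Study 1 shares of records in the WILLOW and control arms. Without a Study term, the expected bias in the condition effect is

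bias = d x (pW - pC).

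- For Condition effects, d is the between-study difference in outcome level.
- For Time X Condition effects, a constant shift between studies cancels when change from baseline is taken. Here d is the between-study difference in change.
- If pW = pC, the bias is zero whatever d is.

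**Step 2: range.** Assume d from 0.2 to 0.5 and a share gap from 0.05 to 0.30. For a two-sided 5% test with independent records, SE = sqrt(2/n) for n per arm, and the rejection rate under no effect is Φ(bias/SE - 1.96) + Φ(-bias/SE - 1.96).

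| d (SD) | pW - pC | Bias (SD) | Rejection rate, 50 per arm | Rejection rate, 100 per arm |
|---|---|---|---|---|
| any | 0 | 0 | 0.050 | 0.050 |
| 0.2 | 0.05 | 0.01 | 0.050 | 0.051 |
| 0.3 | 0.20 | 0.06 | 0.060 | 0.071 |
| 0.5 | 0.20 | 0.10 | 0.079 | 0.109 |
| 0.5 | 0.30 | 0.15 | 0.117 | 0.186 |

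**Step 3: does the term repair it?** Simulation with 4,000 runs, 100 records, 30 of them from Study 1, and no true condition effect:

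| Records WILLOW/control, Study 1; Study 2 | pW - pC | d | Without Study: mean effect, rejection rate | With Study: mean effect, rejection rate |
|---|---|---|---|---|
| 15/15; 35/35 | 0 | 0.5 | 0.006, 0.049 | 0.006, 0.054 |
| 21/9; 29/41 | 21/50 - 9/50 = 0.24 | 0.5 | 0.115, 0.087 | -0.005, 0.055 |
| 20/10; 30/40 | 20/50 - 10/50 = 0.20 | 0.3 | 0.059, 0.066 | -0.002, 0.054 |

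The unadjusted means agree with the formula: 0.5 x 0.24 = 0.12 and 0.3 x 0.20 = 0.06.

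**Step 4: cost if the shares are balanced.** Leaving Study out multiplies the residual variance by 1 + d² x p(1 - p), where p is the overall Study 1 share. With d = 0.2 and p = 0.2 this is 1 + 0.04 x 0.16 = 1.006. With d = 0.5 and p = 0.5 it is 1 + 0.25 x 0.25 = 1.0625. The loss is 0.6% to about 6%.

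**Step 5: how large a share gap could chance produce?** With 50 records per arm and a 30% Study 1 share, the SD of pW - pC is sqrt(2 x 0.3 x 0.7/50) = 0.092. If a design effect of 1.8 applied to it, it would be sqrt(1.8) x 0.092 = 0.12. A 30-point gap is then 0.30/0.092 = 3.3 or 0.30/0.12 = 2.5 chance SDs, so the bottom row of the first table needs a systematic cause.

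**Step 6: two software versions.** If the WILLOW effect is θ1 in Study 1 and θ2 in Study 2, the combined estimate is roughly p x θ1 + (1 - p) x θ2. With assumed values p = 0.3, θ1 = 0.2 and θ2 = 0.4 it is 0.06 + 0.28 = 0.34. A Study main effect does not separate the two; a Study x Condition term does.

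**The case against.** The strongest reply is that no bias has been shown. It needs a WILLOW-to-control ratio that differs between the studies. The protocol calls the pilot an RCT and describes the full RCT as half and half. With equal ratios and similar retention, the unadjusted analysis is unbiased and holds its 5% level. Gaps that arise purely by chance under randomisation do not inflate the unconditional error rate. This stands, and it is why the point is conditional.

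Several stronger readings are tempting and go beyond the documents:

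- **That the SAP states pooling.** It does not. Separate analyses, with returning providers counted once in Study 1, would also fit the sentence, though less naturally. If that was done, the SAP should say so and the modelling point falls away.
- **That the model had no Study term.** The SAP lists effects of primary interest, not the whole model. It names no such term, and no more can be said.
- **That the studies came from different eras.** This rests on identifying Study 1 with the pilot, which no passage does.
- **That keeping returning therapists in their old arm unbalances the study mix.** Alone it does not: if all Study 1 records enter, it leaves the pilot's allocation intact. Varying caseloads (2 to 5 patients) and the five-session filter matter only if their effect on the arms differs between studies.
- **That payment amounts changed.** The script shows that gift cards stopped. The feature-review payment is $100 both as a check (Step 7) and as a gift card (Step 8, in text that still refers to the pilot).

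What the reply does not remove is that the SAP gives no counts from which balance could be judged. Its finding of no significant baseline differences between conditions does not address study mix.

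**Conclusion.** The point holds as a conditional one. The SAP's own rule strongly implies that shared-outcome analyses combine two studies, it shows that the battery differed between them, and it names no term that would separate them. If the Study 1 share differs by arm, a between-study difference in level can bias Condition effects, and a between-study difference in change can bias Time X Condition effects. If the shares are equal, only a little precision is lost.

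The size cannot be computed from the documents. The bias of 0.01 to 0.15 SD and the rejection rates up to 0.117 (50 per arm) or 0.186 (100 per arm) rest wholly on assumed differences, share gaps and sample sizes, with independent records. A reader might infer that the reported WILLOW effects are biased; nothing in the documents shows that. This is a worthwhile improvement to the analysis, and the count table would show whether the concern is material.

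**What to change.** 1. Define Study 1 and Study 2, with dates, and say whether their records were combined and for which outcomes.
2. For each outcome, tabulate records by study and condition.
3. In every model that combines the studies, add Study as a fixed factor. For outcomes tested by Time X Condition, also add Study x Time, because a Study main effect alone does not adjust a change comparison.
4. Show the WILLOW effect by study beside the combined estimate, with a Study x Condition sensitivity test (Study x Time x Condition for the change outcomes). This is needed because the software changes affect only the WILLOW arm.

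The cost is one table and a few degrees of freedom: one for Study and, with four assessments treated as categories, three more for Study x Time. The sensitivity test uses a few more and will have low power, so the by-study estimates should be read alongside it. No new data are needed.
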